#### 4.3.2.1 Patient Inclusion Criteria

Since this is an observational cohort study conducted in a naturalistic setting, open patient entry criteria apply to maximise external validity. General inclusion criteria are: ‡‡‡‡

- age 18 years or above after study start§§§§
- index date on or after study start
- signed, informed consent
- patients treated for DVT or PE
- patients with non-valvular AF ( with one or more risk factors) treated for prevention of stroke and systemic embolism

# 4.3.2.2 Patient Exclusion Criteria

Specific exclusion criterion for the alternative anticoagulant therapy cohort is:

- Any use of univalent direct thrombin inhibitor or direct factor Xa inhibitors.
- use of anticoagulant therapy or other vitamin K antagonists recorded within one year prior to index date.\*\*\*\*\*

# 4.3.2.3 Evaluable patients.

Evaluable patients are those patients who have provided consent and for whom analysable clinical data has been provided in the data collection questionnaires. Evaluable patients for whom the second phase (12 week) survey questionnaire (from BOTH specialist HCP and GP) is returned blank (contain no clinical information) or has not been returned will only be included for analysis of secondary objectives (i) and, (ii).

Consented patients will not be considered evaluable if the specialist HCP reports that the patient did not take rivaroxaban or alternative anticoagulant therapy. If there is evidence to suggest duplication of patients, either through inadvertent duplication between different specialist HCPs within the same clinical setting, or if a patient was switched from rivaroxaban to alternative anticoagulant therapy, or there is a significant delay (>1 month) in receipt of phase 1 survey form then the patients identified will be considered for inclusion on a case by case basis by the study manager and/or project advisory committee.

<sup>1111 Any cases in which there is ambiguity relating to the indication for treatment will be reviewed on a case by case basis, in order to confirm the prescribing indication/indications.

<sup>§§§§ However, a patient under the age of 18 will be included in the study if, in what is expected to be rare situations, a doctor decides on the basis of his/her clinical judgement to prescribe rivaroxaban for such person. \*\*\*\*\*\* patients will be excluded if they are being treated with antiplatelet therapy exclusively

Patients will be automatically withdrawn if the patient or specialist HCP provides informed written or verbal notification that they no longer wish to participate at any stage of the study.

### 4.4 Data Collection

Medical charts-based data collection in this study will be conducted in various phases; relevant documentation (such as information leaflets, questionnaire, consent forms, etc) will be available both as hard copies and electronically for download by the participating specialist HCP.

#### 4.4.1 Data Collection Methods

#### 4.4.1.1 Recruitment

The first phase will have two parts.

Part 1: Recruitment of eligible specialist HCP.

Demographic and prescribing preference data on specialist HCPs (see below) will be collected upon registration with the DSRU. The DSRU will allocate a unique HCP study reference number to each participating specialist HCP for study audit and data management processes.

Part 2: Recruitment of eligible patients initiated with the study drug under clinical care of participating specialist HCP.

For all eligible patients invited to participate, the specialist HCP will be asked to create a patient log to record anonymously (using the study patient reference number provided on patient study documentation issued), demography (age and sex), indication, treatment given and presence of known pre-existing risk factors for stroke and bleeding as derived from data within existing medical charts. This log will be submitted to the DSRU coordinating centre either through a secure online website, or via surface mail. The unique study reference number allocated to each patient will be used for study audit and data management processes.

#### 4.4.1.2 Exposure/outcome data collection

The second phase will also have two parts.

Part 1: At least twelve weeks post index date, the specialist HCP will be prompted to complete a questionnaire which will gather information recorded within medical charts on medical history and medication use prior to or present on index date; changes on general health and medications during treatment, clinical events of medical interest and serious

adverse event reports [classified using the International Conference on Harmonisation definitions [36]]. For patients for whom the specialist HCP reports that the patient was discharged to primary care for continued treatment during the 12 week observation period, the patient's GP will be contacted to complete an abridged end of survey 12 week questionnaire using data recorded within primary care medical charts.

Part 2. Events of interest will undergo aggregate assessment of drug-relatedness, which may include follow-up using event-specific questionnaires sent to the specialist HCP (see 4.4.2.3) or GP. These events will be assessed for drug-relatedness by DSRU staff.[37] With the exception of these enquiries for additional information on selected events, no further monitoring of patients for purposes of data collection for this study from medical charts will occur post the survey period.

## 4.4.2 Data Collection

## 4.4.2.1 Specialist HCP

The following data will be collected for specialist HCPs upon recruitment into the study

1. Demographic characteristics; (age, sex, ethnicity, year of first registration as HCP and awarding institution, year of first registration as specialist and awarding institution, year of start of employment at current institution)

2. Setting- (e.g. inpatient hospital ward, outpatient clinic);

3. Institution type (teaching, general, private) and region of location

4. Specialist HCP preference factors (type of novel anticoagulants prescribed in previous calendar month; proportion of novel anticoagulant use of all anticoagulants prescribed in previous calendar month)

5. Participation response/non-response rates (of eligible specialist HCPs within relevant existing research networks where available).

## 4.4.2.2 Eligible patient index date information

For all eligible patients invited to participate, the following anonymised information will be collected using information contained within medical charts.

- o demographic characteristics (age, gender)
- Reasons for prescribing (clinical judgement, recommendation from NICE, expert committee guidelines, trust formulary committee guidelines, Patient Group Direction in anticoagulation clinic, potential ease of reversibility of anticoagulant, lifestyle

(anticoagulant monitoring needs), patient non-adherence with prior anticoagulant therapy, side-effects with prior anticoagulant therapy.

- $\circ$  which anticoagulant regimen was prescribed and start date
- o clinical condition requiring anticoagulation (indication)
- Prior anticoagulation treatment
- Stroke and Bleeding risk factors
  - Congestive Heart Failure/Left Ventricular Dysfunction
  - o TIA/Thromboembolism History
  - Previous History of Stroke
  - Vascular Disease History (previous MI, peripheral arterial disease or aortic plaque)
  - History of Hypertension
  - Current Hypertension
  - Uncontrolled BP, > 160mmhHg systolic at time of treatment initiation
  - o Medication Usage Predisposing to Bleeding (Antiplatelet agents, NSAIDs
  - Labile INR (Unstable/high INRs)
  - Diabetes Mellitus
  - Alcohol Abuse or Excess†††††
  - ο Renal Disease (Dialysis, transplant, Cr >200 μmol/L)
  - Abnormal Liver Function (Cirrhosis, Bilirubin >2x Normal, AST/ALT/ALP >3x Normal)
  - Prior Major Bleeding or Predisposition to Bleeding

## 4.4.2.3 Patient 12 week end of observation questionnaire

For evaluable patients providing consent and for whom a completed index date questionnaire has been received by the DSRU, after at least 12 weeks of observation, a second questionnaire will be systematically generated to collect clinical information relevant to start of observation and any clinical events of medical interest (including serious adverse event reports [classified using the International Conference on Harmonisation definitions [36]] as recorded in the medical charts during the first 12 weeks of observation.

Data obtained from the 12-week end of observation questionnaire will include:

• Additional information on anticoagulation treatment regimen:

<sup>+++++ Alcohol abuse/excess is classified as intake greater than current recommendation by the NHS guidelines of > 21 units for men or > 14 units for women per week

- details of prior use of oral and parenteral anticoagulant therapy (thienopyridines, aspirin, glycoprotein IIb/IIa inhibitors, heparins)
- If switching anticoagulant to either study drug: details of transition plan (both of prior anticoagulant and either study drug); Reasons for switching.
- Treatment regimen during the 12 weeks observation period (number of prescriptions issued (with dates, posology and duration) if known)
- Dates and reasons for changes in anticoagulant treatment regimen during 12 week observation period‡‡‡‡‡
- All relevant laboratory blood parameters during two-week observation period pre-index date and during 12 week observation where applicable (haemoglobin, platelet count, baseline clotting screen (PT, APTT, Fibrinogen Derived, D-Dimer) [*NB abnormalities would be reported as events*]
- If study drug stopped: date and reason for stopping, details of transition plan to alternative anticoagulant of study drug stopped; if required, details of reversal of anticoagulation therapy and management of bleeding complication.
- Recent ( < 4 weeks prior to index date) and concomitant medications (at index or during treatment):
  - not recommended for concomitant use (including azole antimycotics [e.g. ketoconazole] and HIV protease inhibitors)
  - to be used with caution (including fluconazole, strong CYP3A4 inducers, P-gp inhibitors, non-steroidal anti-inflammatory drugs (NSAIDs), acetylsalicylic acid, oral steroids, hormone and oral contraceptive therapy, platelet aggregation inhibitors or other antithrombotic agents)
- Medical history relevant for important potential, identified and special risks of interest (plus dates of first diagnosis/report). For example: past history of DVT/PE, myocardial infarction (MI), percutaneous coronary intervention (PCI), coronary artery bypass graft (CABG), other recent surgery within 3 months prior to index date, malignancy, pregnancy, family and/or personal history of congestive heart failure, diabetes mellitus, hypercholesterolaemia, peripheral arterial disease, COPD etc.)
- Specific information on renal function status at index date and any changes during 12 week observation period
- Specific information on hepatic disorders present at index date (cholestasis and jaundice, hepatic failure and associated disorders, hepatic fibrosis and cirrhosis and hepatic viral infections) and any recent abnormal liver function tests.

Version 40 20/11/2014 REC Ref 12/SC/0592

##### for rivaroxaban only

- event reports including selected risks of interest (Table 4)
- o cause and date of death (if died) in the first 12 weeks after starting treatment;
- reported pregnancies at start or during the first 12 weeks after starting treatment and outcome of birth.
- behaviours prior to and/or starting treatment (e.g. smoking, alcohol/substance misuse); treatment adherence

Risk/Missing Information	Proposed data capture	Comment
IDENTIFIED, POTENTIAL AND SPECIAL RISKS A	ND OUTCOMES for targeted data	collection on SCEM questionnaires
Major bleeding episode (into a critical organ	Targeted outcome questions on	Selected risk factors collected on SCEM
sites )	critical sites	questionnaire. Further data on severity,
		management and risk factors to be collected
		via follow-up.
Clinically relevant minor bleeding episodes	Targeted outcome question to	Selected risk factors collected on SCEM
	specify details	questionnaire. Not for follow-up
Incident and recurrent thromboembolic	Targeted outcome questions	Selected risk factors collected on SCEM
complications (DVT, PE, Stroke)		questionnaire. Further data on symptoms,
		severity, management and risk factors to be
		collected via follow-up.
Overdose. accidental trauma and Reversal of	Targeted outcome question	Events of overdose (dose > 50mg/day) and
anticoagulation therapy		accidental trauma are those of clinical
		medical importance which require acute
		medical/surgical treatment (with or without)
		hospitalisation Further data to be collected
	-	via follow-up
Management of homeostasis	Targeted outcome question	Data on management of homeostasis in
		patients reported with events of surgery
		(elective or urgent ) during the observation
Increased liver transaminases and Gamma-	Terreted outcome supption	period will be collected via follow-up
	Targeted outcome question	Data on diagnosis of hepatic failure and where abnormal laboratory results indicate 3
Glutamyl Transferase (GGT)		
		X ULN relevant parameters will be collected via follow-up.
Concomitant use of contraindicated	Targeted outcome question on	Further data may be collected via follow-up
medications and medications to be used with	other medications to gather	i uniner data may be collected via follow-up
caution	duration and changes	
IMPORTANT MISSING INFORMATION for general		
Use during pregnancy and lactation	General event report	Further data to be collected via follow-up
use during pregnancy and lactation		i urtiler uata to be collected via ioliow-up

Table 4.	Selected	events o	f interest	requiring	further	evaluation
I abit T.	Sciette	CVCIILS U	1 mici csi	requiring	i ui uici	cvaluation

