<sup>‡‡ Children and adolescents aged less than 18 years of age will be excluded from the SCEM study. Since this is important missing information, data on this special population will be captured within the complementary M-PEM, if reported.

hypertension, active ulcerative gastrointestinal disease) and off-label groups (patients with other non-orthopaedic medical conditions)

 concomitant use of medications that are contraindicated or to be used with caution (e.g. CYP3A4 inducers/inhibitors, P-gp inhibitors, anticoagulants, aspirin, nonsteroidal anti-inflammatory drugs (NSAIDs), oral steroids, hormone and oral contraception therapy and platelet aggregation inhibitors)

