#### 4.3.2 Phase 2: Selection of patients

The accessible study population will be that portion of the target population of interest to whom participating specialist HCPs have access. The identification of the actual study population, (which will be a subset of the accessible study population) will be through (non-probability) systematic sampling whereby all consecutively identified†††† eligible new user patients treated by any specialist HCP (after the pharmacotherapeutic treatment decision has been made that one of the two study oral anticoagulants is the most appropriate treatment based on clinical need) and who provide consent ( see section 3.0) will be enrolled until the desired sample size is reached. This method will be used because a probability sampling framework is not feasible and because participation within the study is not required as a condition of receiving treatment. This approach is intended to reduce conscious or unconscious selection bias on the part of the specialist HCP as to whom to invite to participate in the study, especially with regard to prognostic factors that may be related to prognosis.

New users of rivaroxaban will be comprised of rivaroxaban naïve patients, who may or may not be antithrombotic or anticoagulant treatment naive patients newly initiated by specialist HCPs. The patient may then have medicines management transferred to the GP in primary care. Thus, the GP may take on the primary role of monitoring treatment, providing prescriptions and altering the dose when necessary, with the option of referral to secondary

<sup>†††† As relevant to the date that the specialist HCP registers to participate in the study

care if and when required. Alternatively, the patient may be primarily managed within the secondary care setting alone.

The contextual cohort will be comprised of patients for whom no exposure to anticoagulation therapy has occurred within the 12 months prior to initiation by the Specialist HCP for the current study. Clinical care pathway will be the same as that outlined above for rivaroxaban patients.

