For major bleeding events not specified in the primary outcome, each of the individual components of the major bleeding criteria ( a fall in haemoglobin of 2 g/dL or more, or a transfusion of 2 or more units of packed red blood cells or whole blood, or a fatal outcome - as per table 2) will be summarised. Where an individual has one or more criterion for an individual organ site of interest, this will also be summarised – in such individuals the first report will be regarded as the incident event.

For clinically relevant non-major bleeding events, each of the individual associated components (as per table 2 such as requiring medical intervention, unscheduled contact (visit or telephone call) with a physician, (temporary) cessation of study drug treatment, or associated with discomfort for the subject such as pain or impairment of activities of daily life) will be summarised. Where an individual has one or more criterion for a clinically relevant non-major bleeding event, this will also be summarised – in such individuals the first event report will be regarded as the incident event.

Analysis of event data for purposes of signal detection includes exploring overall risk and rate for the observation period and time to onset profiles. The methodology provides a numerator (the number of reports of an event) and a denominator (person-time at risk), both collected within a known time frame. This allows for the calculation of crude risks (percent of total valid cohort exposed) and rates (Incidence Densities-ID; person-time incidence rates) for each event separately. Each event may be reported in response to a closed question (for example information on each individual major and/or clinically relevant non-major bleeding risk component), or as free text in response to open questions on the data collection forms. Such analyses will be performed using 'Higher-level' event terms from the MedDRA dictionary where possible. The risk profile of the overall cohorts and sub-group of interest

(based on index date characteristics, including whether anticoagulant naïve, rivaroxaban naïve or past (other anticoagulant user) will be described by presenting summary tabulations (by rank) of counts and incidence risk of reported events, and crude event rates (IDs).

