<sup>§§§§§§§ Ideally, the exposure time would be censored at the time of the first event. However, since there are a large number of health outcomes of interest and the censoring would be different for each outcome, the denominator for the crude ID will not initially include censoring. If an elevated crude ID is identified in this monitoring analysis, a subsequent analysis with appropriately censored denominator will be performed for that outcome.

Sensitivity analyses will examine any under-reporting by including events of interest recorded in primary care medical charts and confirmed on follow-up for those patients discharged to primary care, during the 12 week observation period.

As IDs for the overall cohort may sometimes mask significant signals in specific risk groups, the subgroups defined by specific characteristics (e.g. previous history of VTE or haemorrhage, previous/concurrent use of selected medications, off-label indication groups, rivaroxaban naïve or past user) will have IDs calculated and compared according to strata for relevant events, where appropriate.

It is possible to explore the time taken for an event of interest using parametric time to event models (e.g. Weibull) as described previously, thus providing an additional tool for signal generation purposes. This approach will be explored for events of interest, where counts  $\geq 5$ . If undertaken, a sensitivity analysis will be performed to include in the numerator events reported within 7 days of stopping, and extend the denominator by 7 days

4.7.6 To characterise differences in prevalence of prognostic factors and clinical risk factors for haemorrhage associated with rivaroxaban in comparison with contextual cohort as reported during the first 12 weeks after starting treatment in routine secondary care hospital setting in UK.

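### The 12-week form's prior-therapy item lists antiplatelets as anticoagulants and omits vitamin K antagonists, and the naïve/past-user strata do not separate patients as labelled

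*Supplement*

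**What the plan says.** Section 4.4.2.3 sets out the content of the 12-week questionnaire. Under additional information on the anticoagulant regimen it asks for "details of prior use of oral and parenteral anticoagulant therapy (thienopyridines, aspirin, glycoprotein IIb/IIa inhibitors, heparins", and the bracket closes there.

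The index-date form (section 4.4.2.2) has its own item, "Prior anticoagulation treatment", with no drug list and no look-back period. The same form records antiplatelet agents separately, with NSAIDs, as drugs that predispose to bleeding.

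Section 4.7.5 describes event risks in subgroups "based on index date characteristics", "including whether anticoagulant naïve, rivaroxaban naïve or past (other anticoagulant user". Later in that section, incidence densities are to be compared across strata that include "off-label indication groups, rivaroxaban naïve or past user".

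Section 4.3.2 defines the cohort: "New users of rivaroxaban will be comprised of rivaroxaban naïve patients, who may or may not be antithrombotic or anticoagulant treatment naive patients".

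**The concern.** An item that asks about oral and parenteral anticoagulants should let a coder tell who had an anticoagulant before the index date. This one names mostly drugs of another kind and leaves out the class that the protocol itself describes as standard oral treatment.

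Prior anticoagulant status matters to the secondary objectives. Rivaroxaban patients may be anticoagulant-experienced, while contextual patients must have had no anticoagulant in the preceding 12 months (section 4.3.2). The limitations section (5.2) also expects some patients to be channelled to rivaroxaban because an earlier treatment failed or was poorly tolerated. If prior treatment is recorded badly, the account of who receives rivaroxaban suffers, and so does any split of event rates by prior use.

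**Working it through.** No sample-size or power figure is involved, so the check sets the passages side by side.

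**1. The drug classes**

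| Class | In the 12-week item? | Treatment elsewhere in the protocol |
|---|---|---|
| Thienopyridines, aspirin, glycoprotein inhibitors | Yes, as anticoagulants | Section 2.2.2 lists "anticoagulants, aspirin, nonsteroidal anti-inflammatory drugs (NSAIDs" and platelet inhibitors as separate entries. Section 4.4.2.2 puts antiplatelets under bleeding-risk medication. A footnote to the section 4.3.2.2 criteria treats antiplatelet-only patients as a distinct group to be excluded. |
| Heparins | Yes | Anticoagulant, parenteral |
| Vitamin K antagonists | No | Section 4.3.2.2 counts them with anticoagulant therapy. Sections 1.4.1 and 1.4.2 describe warfarin as standard in AF and as maintenance after DVT. |
| Direct thrombin and factor Xa inhibitors | No | Named in the section 4.3.2.2 exclusion |
| Fondaparinux | No | An initial option for DVT/PE in section 1.4.2 |

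Three of the four listed classes are antiplatelets, and the only anticoagulant listed is not oral. The bracket carries no sign that it is illustrative, although the recent and concomitant medication item in the same section does mark its examples.

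**2. From answer to data.** Section 4.5.2 says exposure and medication use are coded directly from targeted closed-format questions. If the form reproduces the bracket, the listed classes become the coded classes.

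**3. Two patients traced through the forms**

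- *AF patient with prior aspirin only.* The 12-week item, read literally, gives prior anticoagulant therapy. The index-date form gives no prior anticoagulation, with an antiplatelet recorded as a bleeding-risk drug. The two forms disagree.
- *Patient whose warfarin stopped some time before the index date.* The 12-week item has no matching class. The switching item on the same form need not apply, because it covers only patients switching to a study drug. The index-date item should capture the warfarin, but it has no look-back, so capture depends on how the specialist reads it.

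The protocol does not say which form prevails when they conflict. Section 4.5.2 leaves conflicting data to a Data Management Plan.

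**4. The strata in section 4.7.5.** By section 4.3.2 all rivaroxaban patients are rivaroxaban naïve. Of the three labels "whether anticoagulant naïve, rivaroxaban naïve or past (other anticoagulant user", the middle one therefore covers the whole cohort and contains the other two. For the later pair, if past user means past rivaroxaban user, that stratum is empty. If it means past user of another anticoagulant, its members also belong to the rivaroxaban-naïve stratum. Neither reading divides the patients.

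**5. Reach.** The primary analysis (section 4.7.2) counts adjudicated bleeds over patients at risk and does not use prior-anticoagulant status. Its named stratifiers are gender, age, indication and past haemorrhage or VTE. The sample size (section 4.2) does not depend on prior treatment either.

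**The case against.** The strongest reply is that section 4.7.5 bases its subgroups on index-date characteristics and does not cite the 12-week item. The index-date form has an unrestricted prior-anticoagulation item and keeps antiplatelets apart. The 12-week form also asks switchers about their prior anticoagulant without limiting the class, and section 4.7.3 plans INR/APTT patterns for them. The questionnaire itself is not shown, and coding rules sit in an SOP and a Data Management Plan that are not shown either. This largely stands. A reader might infer that the subgroups are misclassified, and the documents do not support that: a correct source exists, and nothing says an aspirin entry is coded as past anticoagulant use. What remains is that the 12-week item is wrong as written and no rule protects the derivation from it.

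A reader might also try to size the error from the appended product information, which reports acetylsalicylic acid treatment in 34.9% of the AF trial's patients. One third of 1700 is about 567 AF patients, and 0.349 × 567 = 198. That figure should not be used. It is reported across both trial arms, it is not prior use in this cohort, and it does not identify patients on aspirin without an anticoagulant. It would also require the index-date form to be ignored.

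On the strata, the later pair is probably shorthand for the earlier list, is one example among several, and applies only where appropriate. That makes an empty stratum an unlikely intention. The labels still fail to separate patients under either reading.

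**Conclusion.** The prior-therapy item contradicts the rest of the protocol: it labels antiplatelets as anticoagulants and omits vitamin K antagonists and other oral anticoagulants. The consequence is a risk to the secondary description of prior treatment and to the naïve/past-user tabulations, wherever the 12-week item is used or conflicts with the index-date item. That risk assumes the form follows the protocol's wording and that coding follows section 4.5.2. Its size cannot be derived, because the documents give no prevalence of prior vitamin K antagonist or antiplatelet use in this population. The direction of any bias in subgroup comparisons cannot be stated either, since nothing shows that errors would be unrelated to outcome. The stratum labels need correction whichever form is used. Severity is minor.

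**What to change.** - Split the section 4.4.2.3 item in two: (a) prior anticoagulants, naming vitamin K antagonists, heparins/fondaparinux, and direct thrombin and factor Xa inhibitors; (b) prior antiplatelets, naming aspirin, thienopyridines and glycoprotein inhibitors.
- Derive anticoagulant-naïve status from the index-date prior-anticoagulation item together with (a), never from (b). State the look-back and which source prevails on conflict.
- Relabel the section 4.7.5 strata as anticoagulant naïve versus prior user of another anticoagulant.

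The cost is form wording, one derivation rule and two label changes. This protocol version is dated 20 November 2014 and recruitment was anticipated from May 2013, so forms may already be in use. In that case the rule can still be fixed before analysis, with returned forms recoded from the drug names where given and from the index-date item otherwise.
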